10.3. General Statistical Considerations

The statistical analyses will be performed using R, version 4.2.2 or higher. Any statistical tests of hypotheses will employ a level of significance of alpha=0.05.

11. SAMPLE SIZE JUSTIFICATION

Assuming a difference in means between groups of 7 (SANDE) and a pooled standard deviation of 6, the study would require a sample size of 16 subjects for each group (total sample size of 32 subjects) to achieve a power of 90% and a level significance of 5%. To increase the study power and account for dropout, the sample size is being increased to 70 subjects (35 in each arm) to thoroughly characterize the performance of the drops.

13. QUALITY COMPLAINTS AND ADVERSE EVENTS

All subjects will be monitored for adverse events over the course of the study. A place to record any adverse event is included on each case report form.

13.1. General Information

An Adverse Event (AE) is any untoward medical occurrence in a subject who is administered. a study treatment regardless of whether or not the event has a causal relationship with the treatment. An AE, therefore, can be any unfavorable or unintended sign (including an abnormal laboratory finding), symptom, or disease temporally associated with the study treatment, whether or not related to the treatment. In clinical studies, an AE can include an untoward medical occurrence occurring at any time, including run-in or washout periods, even if no study treatment has been administered.

13.2. Monitoring for Adverse Events

At each visit, after the subject has had the opportunity to spontaneously mention any problems, the Investigator should inquire about AEs by asking if the patient has any problems.

13.3. Procedures for Recording and Reporting AEs and SAEs

Subsequent to signing an informed consent form, all untoward medical occurrences that occur during the course of the study must be documented on an Adverse Event Form (AEF). A separate AEF must be filled out for each event. When possible, signs and symptoms indicating a common underlying pathology should be documented as one comprehensive event. For each recorded event, the AE documentation must include the onset date, outcome, resolution date (if event is resolved), intensity (i.e., severity), any action with study treatment taken as a result of the event, and an assessment of the adverse event's relationship to the study treatment.

Nonserious Adverse Events

A nonserious AE is defined as any untoward change in a subject's medical health that does not meet serious criteria noted below (e.g., is not life-threatening, does not require hospitalization, does not prolong a current hospitalization, is not disabling, etc.). All adverse events must be reported regardless of whether or not they are related to the study treatment.

For nonserious adverse events, an AEF containing all available information will be collected on a routine basis and submitted to the Medical Monitor at the close of the study.

Serious Adverse Events

A serious adverse event (SAE) is defined as any adverse experience that meets any of the following criteria:

- Results in death.
- Is life-threatening.

NOTE: Life-threatening means that the subject was at immediate risk of death from the reaction as it occurred; i.e., it does not include a reaction which hypothetically might have caused death had it occurred in a more severe form.

- Requires inpatient hospitalization or prolongation of existing hospitalization. NOTE: In general, hospitalization signifies that the individual remained at the hospital or emergency ward for observation and/or treatment (usually involving an overnight stay) that would not have been appropriate in the physician's office or an out-patient setting. Complications that occur during hospitalization are AEs. If a complication prolongs hospitalization or fulfills any other serious criteria, the event is serious. When in doubt as to whether "hospitalization" occurred, the event should be considered serious.
- Results in persistent or significant disability/incapacity. Disability is defined as a substantial disruption of a person's ability to conduct normal life functions. NOTE: The term disability means a substantial disruption of a person's ability to conduct normal life functions. This definition is not intended to include experiences of relatively minor medical significance such as uncomplicated headache, nausea, vomiting, diarrhea, influenza, or accidental trauma (e.g., sprained ankle) which may interfere or prevent everyday life functions but do not constitute a substantial disruption.
- Is an important medical event. An important medical event is an event that may not result in death, be life-threatening, or require hospitalization but may be considered an SAE when, based upon appropriate medical judgment, it may jeopardize the subject and may require medical or surgical intervention to prevent one of the outcomes listed in the definitions for SAEs. Examples of such medical events include allergic bronchospasm requiring intensive treatment in an emergency room or at home, blood dyscrasias or convulsions that do not result in subject hospitalization, or the development of drug dependency or drug abuse.

All available information on a serious adverse event(s) and any other associated AE, if applicable, must be forwarded to the study coordinator for forwarding to the Medical Monitor immediately (i.e., within one working day of the Investigator's or site's knowledge of the event) as follows:

- In studies utilizing EDC (electronic data capture), all available information for the SAE and any associated AE(s) must be entered immediately into the EDC system.
- Additional information for any applicable event is to be reported as soon as it becomes available.

In addition to the reporting of serious adverse events to the study Medical Monitor, the SAE must be reported to the IRB / IEC according to their requirements.

The investigator must document all adverse device events (serious and nonserious but related) and all serious adverse events (related and unrelated) on the Adverse Device Effect and Serious Adverse Event Form. Any device quality complaints will also be documented.

- Both the Quality Complaint Form and the Adverse Device Effect and Serious Adverse Event Form must be e-mailed immediately to the study coordinator.
- Additional relevant information is to be reported as soon as it becomes • available.

12.3.1 Intensity and Causality Assessments

For every adverse event and quality complaint, the investigator must assess the causality as Related or Not Related to the medical device under investigation. An assessment of causality will also be performed by the Medical Monitor utilizing the same definitions, as shown below:

Causality

- Related An adverse event or quality complaint classified as related may be either definitely related or possibly related where a direct cause and effect relationship with the medical device has not been demonstrated, but there is a reasonable possibility that the adverse event or quality complaint was caused by the medical device.
- Not Related An adverse event or quality complaint classified as not related may either be definitely unrelated or simply unlikely to be related (i.e., there are other more likely causes for the adverse event or quality complaint).

Where appropriate, the investigator must assess the intensity (severity) of the adverse event as mild, moderate, or severe based on medical judgment with consideration of any subjective symptom(s), as defined below:

Intensity (Severity)

Mild	An adverse event is mild if the subject is aware of but can easily
Moderate	An adverse event is moderate if the sign or symptom results in
	discomfort significant enough to cause interference with the subject's usual activities
Severe	An adverse event is severe if the sign or symptom is incapacitating and results in the subject's inability to work or engage in their usual activities.

The investigator must document any action taken (i.e., medication, intervention, or treatment plan) and outcome of the adverse event or quality complaint when applicable.

13.4. Follow-Up of Adverse Events and Quality Complaints

The investigator is responsible for adequate and safe medical care of subjects during the study and for ensuring that appropriate medical care and relevant follow-up procedures are maintained after the study. Any additional data from these follow-up procedures must be documented and available to the study coordinator who, with the Medical Monitor, will determine when the data need to be documented on the CRFs.

13.5. Safety Analyses

The type, severity, duration, and frequency of reported ocular adverse events will be tabulated. Adverse events will also be summarized for events that were considered treatment-related.

14. GCP, ICH and ETHICAL CONSIDERATIONS

This study will be conducted in compliance with Good Clinical Practices (GCPs), including International Harmonization (ICH) Guidelines, and in general, consistent with the 1996 version of the Declaration of Helsinki. In addition, all applicable local, state and federal requirements will be adhered to.

This study is to be conducted in accordance with Institutional Review Board regulations. The investigator will obtain appropriate IRB/ethics committee approval prior to initiating the study.

The study will be registered with clinicaltrials.gov.

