10. ANALYSIS PLAN

10.1. Analysis Data Sets

All subjects who are enrolled in the study will be evaluated for safety. Efficacy analyses will be performed based on data from those eyes that complete the study.

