10.2. Statistical Methodology

Analysis will be done on the per protocol population. For monocular outcomes, analysis will be performed on the study eye that was determined by randomization.

Superiority of Systane COMPLETE relative to Walgreens will be established if the mean SANDE score is significantly lower in the Systane COMPLETE group vs. Walgreens group.

Demographics, baseline characteristics, efficacy endpoints, and adverse events will be summarized descriptively. Summaries of these variables will include sample size, as well as the mean, median, standard deviation, minimum and maximum.

Primary Endpoint: Dry eye symptom frequency and severity as measured by the SANDE questionnaire change after 2 weeks of QID use (subject level). Total scores will be compared using a two-sample t-test.

The step-down methodology will be used on the other endpoints in the following order:

- Comparing corneal and conjunctival staining in the study eye before and after 2 weeks of QID use of their assigned drop (eye level). The corneal and conjunctival staining scores will be totaled from the 5 evaluation zones for analysis. Total scores will be compared using a two-sample ttest.
- Comparing Non-invasive TBUT times of the study eye in the two arms of the study, before and after 2 weeks of QID use of their assigned drop (eye level). Time will be compared using a two-sample t-test.
- Dry eye symptom frequency and severity as measured by the SANDE questionnaire after 1 week of QID use (subject level). Total scores will be compared using a two-sample t-test.

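### Section 13.5 confines its detailed adverse event table to ocular events, so a non-ocular event or SAE judged unrelated has no incidence table, and no adverse event summary is specified by arm (minor)

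*Combined protocol and SAP*

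**What the plan says.** **Collection is unrestricted.** Section 13.3 requires an Adverse Event Form for each untoward occurrence after consent, and states: "All adverse events must be reported regardless of whether or not they are related to the study treatment". For serious events, the investigator must document "all serious adverse events (related and unrelated) on the Adverse Device Effect and Serious Adverse Event Form".

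**The safety population is everyone enrolled.** Section 10.1: "All subjects who are enrolled in the study will be evaluated for safety".

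**The detailed safety table is restricted.** Section 13.5 has two sentences. The first reads "The type, severity, duration, and frequency of reported ocular adverse events will be tabulated". The second reads "Adverse events will also be summarized for events that were considered treatment-related"; it is not limited to the eye.

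**The general summary is not restricted, but its statistics do not fit.** Section 10.2: "Demographics, baseline characteristics, efficacy endpoints, and adverse events will be summarized descriptively". It continues: "Summaries of these variables will include sample size, as well as the mean, median, standard deviation, minimum and maximum".

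**The concern.** Collection and analysis have different scopes. The protocol gathers all adverse events, but the section that governs their analysis gives type, severity, duration and frequency for ocular events only. Outside the eye, an event enters a 13.5 summary only if it is judged related. That makes its appearance depend on a causality rating. Tabulating all events by arm serves the opposite purpose: an imbalance can be seen whatever anyone thought of each case.

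The introduction rests the trial on the argument that two drops with the same active ingredient may differ through their inactive ingredients. A complete, arm-level account of adverse events belongs in the results of such a comparison. The plan does not currently promise one.

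**Working it through.** The documents state no adverse event rate, so there is no figure to reproduce. The check follows each class of event through the sections that could place it in the results.

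| Class of event | Recorded (13.3) | 13.5, first sentence | 13.5, second sentence | 10.2 general summary |
|---|---|---|---|---|
| Ocular, related | Yes | Yes | Yes | Yes |
| Ocular, not related | Yes | Yes | No | Yes |
| Non-ocular, related | Yes | No | Yes | Yes |
| Non-ocular, not related (serious or not) | Yes | No | No | Yes |

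1. **Where the gap lies.** Only the last row is missing from both sentences of 13.5. It relies entirely on 10.2.

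2. **What 10.2 gives that row.** The named statistics are sample size, mean, median, standard deviation, minimum and maximum. The occurrence of an event is a yes/no outcome per subject. Its summary is a count of subjects affected and a percentage of the population, and neither is named.

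3. **How the related/not-related line is drawn.** The causality section (numbered 12.3.1, placed within section 13) counts possibly related events as related, which is generous. It also counts events that are merely unlikely to be related as not related, so some uncertain cases fall in the last row. Both the investigator and the Medical Monitor rate causality. Neither that section nor 13.5 says whose rating decides entry to the treatment-related summary.

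4. **Serious events.** They must all be documented and forwarded, but neither 10.2 nor 13.5 names an SAE table. An SAE appears in 13.5 only if it is ocular or judged related.

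5. **By arm.** Neither sentence of 13.5 mentions treatment arms, and nor does the descriptive summary in 10.2. This applies to the ocular table as much as to the rest. It is a separate omission from the ocular restriction, and deleting the word ocular would not cure it.

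**The case against.** The strongest reply is that 10.2 already covers all adverse events. Its list of statistics says what summaries will include, which need not mean only those. The same list is applied to demographics, which usually contain categorical items, so it reads as loose boilerplate and not as a bar to counts. This reply stands in part: 10.2 does promise a summary without an ocular limit. It does not stand as a specification, because it names no count, percentage or arm, and it leaves 10.2 and 13.5 with different scopes.

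Three stronger readings are tempting, and the documents do not support them.

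- *Only ocular events will be summarized anywhere.* The 10.2 summary is general, and the second sentence of 13.5 takes in related events of any body system.
- *A bilateral reaction may be counted twice because both eyes are enrolled.* Section 13.1 defines an adverse event as an occurrence in a subject, and 13.3 asks that signs with a common underlying pathology be recorded as one event where possible. That largely answers the worry.
- *Serious systemic events could go unnoticed.* Section 13.3 sends every SAE to the Medical Monitor within one working day and to the ethics committee under its own rules. This is a gap in the analysis specification, not in surveillance.

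**Conclusion.** The point holds in limited form. The restriction to ocular events in 13.5 is explicit wording, not just missing detail, and it conflicts with the scope of collection in 13.3 and of the general summary in 10.2. As written, a non-ocular event or SAE judged not related has no specified incidence table, and no adverse event summary is specified by arm.

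Severity is minor. The primary endpoint is unaffected, the data will exist, and a careful analyst could build the table at reporting. The documents give no expected rate for non-ocular, unrelated events over the two weeks. Any probability of seeing one among the 35 subjects planned per arm would therefore rest on an assumed rate and would not measure the effect of the wording. The conclusion depends on reading 13.5 and 10.2 literally; if the sponsor intends the 10.2 summary to give counts and percentages by arm, the text only needs to say so.

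**What to change.** **Section 13.5.** Delete the restriction to ocular events. State that, by treatment arm and for all enrolled subjects (the safety population of 10.1), the report will give the number and percent of subjects with at least one event, and the number of events, for:

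- all adverse events;
- ocular and non-ocular events separately;
- serious adverse events;
- treatment-related events.

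Name the population in the text. Section 10.2 opens by placing analysis on the per-protocol population without excepting adverse events. A denominator of subjects who used at least one drop would also depart from 10.1, so it should not be brought in here without changing that section.

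**Section 10.2.** Limit mean, median, standard deviation, minimum and maximum to continuous variables, and specify counts and percentages for adverse events.

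**Cost.** A few sentences in two sections and one extra table from data already collected. No new procedures, visits or subjects are needed.

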15. STANDARD EVALUATION PROCEDURES

Table 15.1. Proposed Visits and Study Assessments

(visits are by patient, with both eyes tested)

Activity	Recruit- ment	Follow-Up	Follow-Up
	Visit 1	Visit 2	Visit 3
Informed Consent	Х		
Demographics	Х		
General Information: Medical History	Х		
Non-Invasive Tear Breakup Time	Х		Х
Slit Lamp Exam and Staining Evaluation	Х		Х
SANDE Questionnaire	Х	Х	Х
Compliance Check		Х	Х
Monitor for Adverse Events		Х	Х
Complete Exit Form ¹			X

¹ Complete Exit Form upon termination of subject participation, or at Visit 3, whichever occurs first.

17. FINANCIAL AND INSURANCE INFORMATION/STUDY RELATED INJURIES

Every effort to prevent study-related injury will be taken by the Study Doctor and staff. In the event a patient is injured as a direct result of the study while following the Study Doctor's instructions and the study requirements, the patient will be instructed to contact his or her doctor immediately. The Study Doctor is to treat the injured subject as needed for those injuries caused directly by this research study. In the event of injury or illness caused by or occurring during a subject's participation in this research study, all charges for medical care provided to the subject will be billed to his or her insurance company. The Study Doctor or Sponsor does not offer to cover the medical care costs for injuries or illnesses that are not caused directly by the research study. The Sponsor does not offer to provide any other compensation, unless specifically agreed to elsewhere in this document. This information will be provided to each study subject before the start of the study in the consent form.

18. STUDY ENDPOINT CRITERIA

18.1. Patient Completion of Study

If a study patient has completed the final visit (Visit 3) of the study, he/she is considered to have completed the study.

18.2. Patient Discontinuation

Each study patient may voluntarily discontinue the study at any time they choose. Study patients who cannot complete the study for administrative reasons (e.g., non-compliance, failure to meet visit schedule, etc.) will be discontinued from the study. Study patients discontinued during the enrollment phase (prior to surgery) of the study will be replaced.

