9.2.4. Exit Procedures

In the event of premature exit from the study, all study related examinations should be completed where possible. The Exit CRF should be completed, noting that the subject did not complete the study and the reason for premature study exit. If no premature exit from the study occurs, the Exit CRF should be completed at the end of Visit 3.

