9.5. Discontinued Subjects

Discontinued subjects are those who do not have an exit visit or who come into the office to be exited prior to the scheduled final study visit. Subjects may be discontinued from the study at any time if, in the opinion of the investigator, their continued participation in the study poses a risk to their health. The reasons for discontinuation include:

- a. Adverse event;
- b. Lost to follow-up;
- c. Subject decision unrelated to an adverse event;
- d. Protocol violation;
- e. Treatment failure;
- f. Other.

To ensure the safety of all subjects who discontinue prior to Visit 3, investigators should assess each subject and, if necessary, advise them of any therapies and/or medical procedures that might be needed to maintain their health. Any changes in medical health and/or use of concomitant medications should also be captured.

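### The protocol does not separate stopping the drop from leaving the study, so discontinued subjects have no assured Day-14 SANDE and are left out of the efficacy analysis

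*Combined protocol and SAP*

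**What the plan says.** Two sections govern how a subject leaves.

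- Section 18.2: "Study patients who cannot complete the study for administrative reasons (e.g., non-compliance, failure to meet visit schedule, etc.) will be discontinued from the study". The verb is mandatory, and the exit is from the study, not from the drop.
- Section 9.5: "Subjects may be discontinued from the study at any time if, in the opinion of the investigator", continued participation poses a health risk. The verb is permissive. The reasons then listed go beyond health risk and include protocol violation and "Treatment failure".

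Section 9.5 also defines the group, by reference to the last planned visit (Visit 3): "Discontinued subjects are those who do not have an exit visit or who come into the office to be exited prior to the scheduled final". On data collection, section 9.2.4 says: "In the event of premature exit from the study, all study related examinations should be completed where possible".

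On analysis, section 10.1 says "Efficacy analyses will be performed based on data from those eyes that complete the study", and section 10.2 says "Analysis will be done on the per protocol population" without defining that population. Section 18.1 defines completion: "If a study patient has completed the final visit (Visit 3) of the study, he/she is considered to have completed the study".

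The primary endpoint (section 10.2) is the change in SANDE after two weeks, compared by a two-sample t-test. Table 9.2-1 puts Visit 3 at Day 14 ± 2 days. Table 15.1 schedules the compliance check at Visits 2 and 3.

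**The concern.** A subject who stops or under-uses the drop can usually still fill in a questionnaire two weeks after randomisation. The protocol makes no provision for this. Once a subject is discontinued, the only further SANDE it calls for is one at exit, where possible, on whatever day exit falls. If non-compliance is noticed at Visit 2, that is about Day 7, outside the primary window.

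This matters because the reasons for leaving may carry information about the outcome. A subject may use the drop less because it stings or does not seem to help, and a subject recorded as a treatment failure has probably done badly on symptoms, which the primary endpoint measures. Section 5 describes the comparator's preservative as a known cause of ocular dryness and staining, so on the protocol's own premise tolerance could differ by arm. If such subjects are missing at Day 14, the two groups compared are no longer the two groups randomised.

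The question is related to the choice of analysis set but distinct from it. The analysis set can be redefined until unmasking; a Day-14 value that was never sought cannot be recovered.

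**Working it through.** **1. The passages side by side**

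| Question | Section 18.2 | Section 9.5 |
|---|---|---|
| Verb | will be | may be |
| Stated ground | cannot complete, for administrative reasons | health risk, in the investigator's opinion |
| Examples or reasons | non-compliance, visit schedule | includes adverse event, protocol violation, treatment failure |
| Drop stopped distinguished from study left? | No | No |
| Day-14 SANDE sought afterwards? | No | No |

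An exit SANDE under 9.2.4 may exist, but 10.1 and 18.1 together keep a subject without Visit 3 out of the efficacy analysis. A poorly compliant subject who does attend Visit 3 could still be excluded under the undefined per protocol population in 10.2.

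**2. The plan's own figure**

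Inputs from section 11: difference 7, SD 6, power 90%, significance 5% (taken as two-sided).

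n per arm = 2 × (1.960 + 1.282)² × 6² / 7² = 15.4, rounded up to 16. The stated 16 per arm (32 in total) is reproduced. The exact t-based value is 16.46, or 17 per arm.

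**3. Loss of numbers is not the problem**

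At 35 per arm the t-based power is 99.8%. With equal losses in both arms:

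| Loss | Per arm | Power |
|---|---|---|
| 10% | 32 | 99.6% |
| 20% | 28 | 99.0% |
| 30% | 24 | 97.7% |

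Enrolment could fall by 1 − 32/70 = 54% before reaching the 32 required. The margin protects power, but it does nothing against selective loss.

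**4. Size of a possible bias**

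Let a fraction p of one arm be removed, with a mean SANDE change differing by d from those kept, whose mean is K. The full-arm mean is (1 − p)K + p(K + d) = K + pd, so analysing only those kept shifts that arm's mean by p × d. Both p and d are assumptions; the documents give neither.

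| p | d = 7 | d = 14 |
|---|---|---|
| 5% | 0.35 | 0.7 |
| 10% | 0.7 | 1.4 |
| 20% | 1.4 | 2.8 |

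For comparison, the standard error of the difference is 6 × √(2/35) = 1.43 with all 35 per arm. The 10-20% rows, 0.7 to 2.8 points, are 10% to 40% of the 7-point design difference.

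**5. Effect on type I error**

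Assume no true difference, SD 6, removal from one arm only, and removed subjects 6 or 12 points worse than those kept. The two-sided rejection rate at nominal 5% is then:

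| Removed | Kept in that arm | Shift (6 / 12 points) | Rejection rate |
|---|---|---|---|
| 5% | 33 | 0.3 / 0.6 | 5.5% / 6.9% |
| 10% | 32 | 0.6 / 1.2 | 6.9% / 12.7% |
| 20% | 28 | 1.2 / 2.4 | 12.1% / 34.2% |

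**The case against.** The other side has several good arguments.

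- **The exit examination.** A reader might infer that discontinued subjects give no SANDE at all. Section 9.2.4 does not support that: it asks for all study examinations at premature exit where possible, and SANDE is one of them. What stands is that an exit SANDE need not fall at Day 14 and is not used for efficacy.
- **The trigger in 18.2.** A reader might infer that any lapse in use, or a Visit 2 outside Day 7 ± 1, forces discontinuation. The rule covers patients who cannot complete, so a subject able to attend Visit 3 arguably falls outside it. No compliance threshold is given, and Table 9.2-1 attaches no consequence to a late visit. Forced exit is one possible reading. Yet neither example in itself prevents completion, so the wording leaves a site to guess.
- **The link to the drop.** A reader might infer that these exits are caused by the assigned product. The protocol calls them administrative and nowhere ties them to treatment, and a missed visit may have nothing to do with it. The link is plausible, not documented.
- **The list in 9.5.** Treatment failure is not in 18.2, and the list may only be categories for recording why a subject left. Likewise, the two verbs may address different situations. That softens the conflict, but the list still goes beyond the health-risk ground that introduces it.
- **Size and direction.** The illustration rests on assumed values and on removal from one arm only. At p = 5% the shift is at most 0.7 points, about half the standard error. If poor responders leave the comparator arm, that arm looks better than it was and the bias works against the superiority claim.
- **Dependence on the analysis set.** Day-14 values collected after the drop is stopped change nothing if the completer and per protocol restrictions exclude them. This is correct, and the fix has to cover it.

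**Conclusion.** The point stands in a limited form. Sections 9.5 and 18.2 are not aligned on when a subject leaves the study. Neither separates stopping the drop from leaving the study, no Day-14 SANDE is assured after discontinuation, and the efficacy analysis leaves non-completers out. The primary comparison can therefore be biased if exits are related to symptoms and differ between arms.

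The direction is unknown and the documents give no size. Under the assumed 10-20% removal from one arm and 7-14 point difference, the shift runs from about half to about twice the standard error (0.7/1.43 = 0.5; 2.8/1.43 = 2.0). If exits are few, balanced between arms or unrelated to symptoms, the effect is small or absent. The documents do not support saying that no outcome is collected, that every lapse compels exit, or that exits are due to the drop. The change should be made before enrolment, because the missing values cannot be obtained later.

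**What to change.** 1. Reconcile sections 9.5 and 18.2 so that a site can tell when a subject leaves the study and which section governs. Which grounds apply is for the sponsor and investigator to decide.
2. In sections 9.2.4 and 9.5, distinguish a subject who has stopped the study drop from one who has left the study. Unless consent is withdrawn, still seek the SANDE at Day 14 ± 2, with staining and TBUT if the subject is willing. Record it on the Visit 3 CRF with the date of last drop.
3. In sections 10.1 and 10.2, state that these Day-14 values enter an as-randomised analysis of the primary endpoint. Without this step the extra data would not affect the result.

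The cost is protocol wording and one CRF field. Visit 3 and the questionnaire are already scheduled, so there is no new procedure and no additional subject. The small downside is that including poorly compliant subjects may slightly dilute the estimated difference. On the plan's own assumptions, power of 99.8% at 35 per arm leaves ample room for that.
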